**Table 1 Time point response for subjects with target (+/- non-target) lesions**

Target Lesions	Non-Target Lesions	New Lesions	Overall Response
CR	CR	No	CR
CR	Non-CR / Non-PD	No	PR

CR	NE	No	PR
PR	Non-PD or not all evaluated	No	PR
SD	Non-PD or not all evaluated	No	SD
Not all evaluated	Non-PD	No	NE
PD	Any	Yes or No	PD
Any	PD	Yes or No	PD
Any	Any	Yes	PD

CR = complete response; PR = partial response; SD = stable disease; PD = progressive disease; NE = inevaluable

**Table 2 Time point response for subjects with non-target disease**

Non-Target Lesions	New Lesions	Overall Response
CR	No	CR
Non-CR / Non-PD	No	Non-CR / Non-PD (1)
Not all evaluated	No	NE
PD	Yes or No	PD
Unequivocal PD	Yes or No	PD
Any	Yes	PD

CR = complete response; PR = partial response; SD = stable disease; PD = progressive disease; NE = not evaluable

(1) Non-CR / non-PD is preferred over 'Stable Disease' for non-target disease since SD is increasingly used as an endpoint for assessment of efficacy in some trials. To assign this category when no lesions can be measured is not advised.

### **Confirmation of Response**

To be assigned a status of complete or partial response, changes in tumor measurements must be confirmed by repeat assessments performed not less than 4 weeks after the initial criteria for response are first met. In the case of SD, measurements must have met the SD criteria at least once

after study entry at a minimum interval (in general not less than 6 – 8 weeks) that is defined in the study protocol. Best overall response thus can be interpreted as shown in the Table below (Eisenhauer et al, 2009).

**Table 3 Best overall response when confirmation of CR and PR required**

Overall Response First Timepoint	Overall Response Subsequent Timepoint	BEST overall response
CR	CR	CR
CR	PR	SD, PD, OR PR
CR	SD	SD provided minimum criteria for SD duration are met. Otherwise PD
CR	PD	SD provided minimum criteria for SD duration are met. Otherwise PD
CR	NE	SD provided minimum criteria for SD duration are met. Otherwise NE
PR	CR	PR
PR	PR	PR
PR	SD	SD
PR	PD	SD provided minimum criteria for SD duration are met. Otherwise PD
PR	NE	SD provided minimum criteria for SD duration are met. Otherwise NE
NE	NE	NE

CR = complete response; PR = partial response; SD = stable disease; PD = progressive disease; NE = not evaluable

Appendix E of the protocol provides details on methods of measurements, documentation and evaluation of target / non-target lesions.

### **Time to Response**

The Time to Response will be the time between initiation of treatment and first documentation of PR or CR.

### **Duration of Response**

The duration of response will be the time from first documented response (CR or PR) until the earlier of either first documented tumor progression (PD) or death from any cause. Subjects achieving a CR or PR, who are alive without progression, are lost to follow up, or who have died without report of

progression as of the time of analysis will be censored at the date of last response assessment or last date on study, whichever is earliest.

### **Progression-Free Survival (PFS)**

Progression-free survival will be defined as the time from date of initiation of treatment until the earlier of either first documented tumor progression (PD) or death from any cause. Subjects alive without progression or lost to follow-up at the time of analysis will be censored at the date of last response assessment. Progression free survival will be analyzed at 4.5 months (Stage 2).

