### **Overall Response Rate (ORR, Investigator Assessment)**

The tables below provide time point overall responses for all possible combinations of tumor responses in subjects with target and non-target lesions, with or without new lesions, per RECIST v1.1.

A summary of the overall response status calculation at each time point is presented in Table 1 for subjects who have measurable lesions at baseline, and in Table 2 for subjects who have only non-measurable (therefore non-target) lesions at baseline. For data display and analysis purposes, the “BEST” overall response for each subject from all post-baseline time point overall responses will be used. The best overall response is the best response recorded from the start of the treatment until disease progression/recurrence, or occurrence of intolerable toxicity, whatever comes first, taking, for target lesions, as reference for progressive disease, the smallest sum of diameters of target lesions recorded since the treatment started.

When no imaging/measurement is done at all at a particular time point, the subject will not be evaluable (NE) at that time point. If only a subset of lesion measurements are made at an assessment, usually the case is also considered NE at that time point, unless a convincing argument can be made that the contribution of the individual missing lesion(s) would not change the assigned time point response. Overall Response Rate (ORR) will be defined as the proportion of subjects with a best overall response of Complete Response (CR), Partial Response (PR), or Stable Disease (SD).

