#### **9.1.1 Progression-Free Survival**

Progression-free survival (PFS) will be defined as the date treatment starts to the date of first documented disease progression (PD) or death due to any cause, whichever comes first. Subjects alive without disease progression or lost to follow up at the time of analysis will be censored at the date of last response assessment. Table 1 below shows the censoring rules for progression-free survival.

The distribution of the progression-free survival will be estimated and graphed using Kaplan-Meier method. If applicable, estimates of the 25th percentile, median and 75th percentile and their respective 95% confidence intervals will be provided.

Kaplan-Meier curves for RX-0201 in combination with everolimus and everolimus alone will be estimated separately but displayed on one graph as a visual comparison of the survival curves between treatment groups. The log-rank test will be performed to compare the survival curves at the 0.05 significance level.

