**Table 1 Censoring Rules for Progression-Free Survival**

Situation	End Date	Censored
Documented PD during the study	Date of the first assessment of the series of the tests that determined PD	No
Death during the study before PD	Date of death	No
Discontinued due to PD, but no documented PD	Date of observation of clinical progression (tumor timepoint response assessment CRF page) or date of discontinuation.	No
No baseline assessments	Date of randomization	Yes
Treatment discontinuation for other than PD or death, and no post-baseline tumor assessments	Date of randomization	Yes
Treatment discontinuation for other than PD or death with post-baseline tumor assessments	Date of last tumor assessment	Yes
Death or PD after two or more missed tumor assessments	Date of last tumor assessment before missed tumor assessment	Yes
Subjects still on treatment without PD as of data cut-off	Date of last tumor assessment	Yes
Only NE assessments after CR, PR, SD	Date of last tumor assessment before NE assessment	Yes

Note1: During the study includes Stage 2 treatment phase and follow-up period.

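### The PFS censoring rules do not cover subjects whose post-baseline assessments are all not evaluable, and the general sentences in SAP 4.3 and 9.1.1 do not match the censoring table (minor)

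*SAP*

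**What the plan says.** Four parts of the SAP bear on the censoring date.

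- **General rule.** SAP 4.3, Progression-Free Survival: "Subjects alive without progression or lost to follow-up at the time of analysis will be censored at the date of last response assessment". SAP 9.1.1 gives the same rule. Neither sentence says that the assessment must be evaluable.
- **What NE means.** SAP 4.3, Overall Response Rate: "When no imaging/measurement is done at all at a particular time point, the subject will not be evaluable (NE) at that time point". The same paragraph usually makes a time point NE when only some of the lesions were measured. SAP 9.1.2 lists NE as a response category.
- **Censoring table.** SAP 9.1.1 adds: "Table 1 below shows the censoring rules for progression-free survival". Its last row covers "Only NE assessments after CR, PR, SD" and gives the end date as "Date of last tumor assessment before NE assessment". Two other rows, for "Treatment discontinuation for other than PD or death with post-baseline tumor assessments" and for subjects still on treatment without PD at the data cut-off, use the date of the last tumor assessment with no condition on evaluability. The row for "Treatment discontinuation for other than PD or death, and no post-baseline tumor assessments" uses the date of randomization.
- **Duration of response.** SAP 4.3 says that responders alive without "progression as of the time of analysis will be censored at the date of last response assessment or last date on study", whichever is earliest. SAP 9.1.4 uses the last response assessment. No table applies to this endpoint.

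**The concern.** An NE assessment gives no information about progression. If its date is used for censoring, the subject stays in the Kaplan-Meier risk set across scans at which progression could not be seen. The denominator is then too large at those scans, and the estimate moves upward. The shift always goes in the same direction, and the confidence interval does not reflect it.

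PFS at 4.5 months is the Stage 2 primary efficacy endpoint, estimated from up to 20 combination subjects, so one subject carries about 5% of the weight. The SAP also promises methods fixed before database lock. Where the general sentence and the table can be read to give different dates, two programmers could derive different results from the same data.

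**Working it through.** **1. The plan's own precision figure.** Protocol 9.3 gives half-widths of at most 0.20 (n = 20) and 0.28 (n = 10) for a two-sided 90% interval. The exact Clopper-Pearson interval at p = 0.5 gives 0.198 and 0.278, so the figures reproduce. They do not depend on the censoring rule.

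**2. Which rule applies to which subject.**

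| Pattern of assessments | Row of Table 1 that fits | Censoring date |
|---|---|---|
| CR, PR or SD, then only NE | NE row | Assessment before the NE |
| All post-baseline assessments NE; stopped for a reason other than PD or death, or still on treatment | Not the NE row (no earlier CR, PR or SD); not the no-assessment row (a dated assessment exists); so the general rows | The NE date |
| Non-CR/Non-PD, then only NE | NE row does not name this category | Unclear |
| Confirmed response, then only NE (duration of response) | No table | Last response assessment, which may be NE |

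The third pattern can occur. Protocol 4.2 admits measurable or evaluable disease, SAP 4.3 Table 2 advises against calling the stable state SD when no lesion can be measured, and SAP 7.2.1 puts all efficacy endpoints on the Full Analysis Set. SAP 13 assigns the PFS plot to the set evaluable for tumor response, which requires a measurable lesion. If that set were used for PFS, the third pattern would drop out and the second would remain.

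A subject with SD then NE who stops or stays on treatment also fits a general row as well as the NE row. The table states no precedence, though the specific row is the natural one.

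**3. Size for all-NE subjects.**

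Inputs from the documents: 20 combination subjects; scans every 6 weeks, so days 42, 84 and 126 fall before 4.5 months (4.5 × 30.44 = 137 days); medians of 9 and 4.5 months (Protocol 9.3). Assumptions: exponential PFS, PD dated at the scan, no other censoring before day 137, and k all-NE subjects with their last NE at day t.

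Compare censoring at day t with censoring at the start. Up to t, the k subjects are at risk without a scan-detected event. After t, the curve falls at the same rate under both rules. The difference at day 137 is therefore

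(k/20) × (1 − S(t)) × S(126)/S(t).

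S(42), S(84) and S(126) are 0.899, 0.809 and 0.727 for the 9-month median, and 0.809, 0.654 and 0.529 for the 4.5-month median.

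- Day 42, 9 months: (1/20) × 0.101 × 0.727/0.899 = 0.004
- Day 126, 9 months: (1/20) × 0.273 = 0.014
- Day 42, 4.5 months: (1/20) × 0.191 × 0.529/0.809 = 0.006
- Day 126, 4.5 months: (1/20) × 0.471 = 0.024

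In percentage points:

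| Last NE | Median | k = 1 | k = 2 | k = 3 |
|---|---|---|---|---|
| Day 42 | 9 months | +0.4 | +0.8 | +1.2 |
| Day 126 | 9 months | +1.4 | +2.7 | +4.1 |
| Day 42 | 4.5 months | +0.6 | +1.3 | +1.9 |
| Day 126 | 4.5 months | +2.4 | +4.7 | +7.1 |

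A simulation with k = 1 gave the same per-subject differences.

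**4. Does the proposed rule remove the bias?** A separate simulation (n = 20, 4,000 runs per scenario, a 3% to 15% chance per scan that follow-up ends in one or two NE scans, independent of progression) censored every subject at the last assessment before the NE, or at the start if there was none. Mean 4.5-month estimates were 0.723 to 0.730 against a true 0.727, and 0.526 to 0.532 against a true 0.529. Last-evaluable censoring is unbiased under these assumptions.

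**The case against.** The strongest reply is that the SAP already deals with NE. Section 9.1.1 follows its general sentence with a table, and the NE row does what a reviewer would ask for. This stands for NE after CR, PR or SD.

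A reader might infer from 4.3 alone that every trailing NE is credited as progression-free time. The same simulation puts the effect of that reading at about 0.01 to 0.06 (9-month median) or 0.01 to 0.10 (4.5-month median). The documents do not support it, because the specific row governs the usual case. For example, a subject with SD at week 6 and NE at weeks 12 and 18 would be censored 84 days later under the general sentence, but only if the NE row were ignored. Nor does the SAP say that an unimaged visit supplies a censoring date: with no scan there is no scan date to use. The realistic source is a dated scan with too few lesions measured.

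Other points on that side:

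- Three uninterpretable scans in a row would be unusual, since Protocol 7.6 requires imaging results to be reviewed before the next cycle. This is fair, so the day-126 figures are an upper case and the day-42 figures belong beside them.
- NE subjects can still contribute events: death counts, and so does discontinuation for PD without documented PD. This stands, subject to the table's missed-assessment rule for deaths. The calculation concerns only subjects who end up censored.
- Non-CR/Non-PD can be read as the SD of non-target disease. That is reasonable, but the row should say so.
- The shifts are small beside the planned half-width of 0.20, and SAP 7.3.5 calls any tests exploratory. This supports a low severity. It does not justify leaving the rule open.
- Duration of response is secondary and descriptive, and no size can be given for it.

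**Conclusion.** The point holds as a minor gap. Table 1 treats NE after CR, PR or SD correctly. It leaves all-NE subjects censored at the NE date, does not name Non-CR/Non-PD in the NE row, and does not extend to duration of response. The general sentences in 4.3 and 9.1.1 omit the evaluability condition, and 4.3 does not refer to the table.

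The effect on 4.5-month PFS is upward: about 0.4 to 1.4 points per all-NE subject under a 9-month median and 0.6 to 2.4 under a 4.5-month median. This rests on exponential PFS, 20 subjects and the assumed date of the last NE. The documents give no NE frequency, so the total may be zero. They do not support a claim that the primary estimate is inflated, only that the rule allows it to be.

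**What to change.** - In SAP 4.3 and 9.1.1, for PFS, and in 4.3 and 9.1.4, for duration of response, censor at the last evaluable tumor assessment, defined as CR, PR, SD or Non-CR/Non-PD and not NE. Use the same term in the Table 1 rows that now refer to the last tumor assessment.
- For PFS, treat a subject with no evaluable post-baseline assessment like one with no post-baseline assessment. Use one start date in all such rows. It should be first dose, to match the PFS definition; the table now says randomization, which Stage 2 no longer uses for new subjects.
- Keep the NE row, extend it to Non-CR/Non-PD, and state that it takes precedence over the general rows.
- Cross-reference Table 1 from 4.3.

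The cost is SAP wording and one programming condition, with no new data. If all-NE subjects occur, the estimate will be slightly less favourable and its interval slightly wider.

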## **5 Study Methods**

### **5.1 General Study Design and Plan**

This is a 2-stage phase 1b/2, multi-center, open-label study to assess the safety and tolerability of RX-0201 in combination with everolimus versus everolimus alone to treat subjects with advanced renal cell carcinoma. Approximately 32 subjects will be recruited and enrolled into the study over 20 centers in the US.

Stage 1 is an open-label, dose-escalation phase 1b study of RX-0201 to identify a safe and tolerable dose of RX-0201 up to a target dose of 250 mg/m^2/day when given in combination with everolimus. Approximately 9 subjects will be enrolled to receive the combination of everolimus and RX-0201 at increasing doses of RX-0201 to the MTD or up to a target dose of 250 mg/m^2/day. The number of subjects enrolled into Stage 1 will vary depending upon the number of dose levels needed to determine the MTD, up to a target dose of 250 mg/m^2/day.

Stage 2 is an open-label, 2-arm phase 2 study of RX-0201 in combination with everolimus versus everolimus alone. Approximately 3 additional subjects will be treated with everolimus alone arm and up to 20 subjects in the everolimus/RX-0201 arm.

Everolimus will be administered daily at 10 mg orally at approximately the same time each day consistently with or without food per the approved label instructions in Stage 1 and Stage 2.

RX-0201 will be administered at a starting dose of 125 mg/m^2/day, by a 24 hour continuous intravenous infusion for 14 days followed by 7 days of rest in each 21 day cycle. RX-0201 doses in Stage 1 will be escalated until a maximum tolerated dose (MTD) or a target dose of 250 mg/m^2/day is reached. The MTD or the target dose will be tested further in Stage 2.

For subjects assigned to receive RX-0201 and everolimus, a cycle will be defined as the period elapsing from the first day of RX-0201 administration through Day 21 of the cycle or to the recovery

from any adverse events sufficient that a new cycle of therapy can be administered (e.g., on Day 29 or Day 36), whichever occurs later. Once a new cycle starts, the prior cycle is considered to be completed. For subjects assigned to the everolimus only arm, a cycle will be defined as the period elapsing from the first day of everolimus administration through Day 21 of the cycle or to the recovery from any adverse events sufficient that a new cycle of therapy can be administered, whichever occurs later. Subjects in Stage 1 and Stage 2 may receive up to 8 cycles of combined therapy until withdrawal of consent, pregnancy, substantial noncompliance with study procedures, intolerable adverse event, documented radiological disease progression or death, principal investigator judgment that it is in the best interest of the subject to stop treatment, or study discontinuation. Subjects, who the principal investigator feels are receiving benefit, may continue to receive additional cycles of therapy following discussions with the Sponsor. Subjects randomized to the everolimus only treatment arm will complete the study after 8 cycles but may continue to receive everolimus off-study.

Each subject should complete all study procedures in approximately 8 months (i.e., screening period up to 14 days; treatment period up to eight 21-day cycles, safety follow-up approximately 30 days after the last dose of study medication). However, for subjects approved to receive additional treatment cycles, the duration may be longer than 8 months. The study duration is estimated at approximately 30 months.

## **5.2 Equivalence or Non-Inferiority Studies**

No equivalence or non-inferiority test will be conducted in the analysis.

## **5.3 Inclusion-Exclusion Criteria and General Study Population Defined**

### **5.3.1 Inclusion Criteria**

#### **Disease Related**

- Documented histological or cytological diagnosis of renal cell cancer with a clear-cell component
- Measurable or evaluable disease defined by Response Evaluation Criteria for Solid Tumors (RECIST) ver. 1.1
- Must have received at least one course of therapy with a VEGFR-targeting tyrosine kinase inhibitor (eg, sorafenib, sunitinib, axitinib, pazopanib or tivozanib) and progressed within 6 months of planned first dose of study treatment.
- Prior therapy with cytokines (i.e., IL-2, Interferon) and/or VEGF-ligand inhibitors (i.e., bevacizumab) are permitted
- Prior vaccine therapy in the adjuvant setting is permitted
- Tissue blocks or tissue sections from initial diagnosis or upon diagnosis of advanced metastatic disease will be available for submission to the central laboratory within

approximately 4 weeks after initiation of study treatment; exceptions (e.g., histology determined by fine needle aspirate or tissue is no longer available) require written documentation of why a sample is not available and prior approval by the sponsor before enrollment/ randomization

- ECOG performance status of 0, 1 or 2
- Life expectancy > 3 months

### **Demographic**

- Males and females  $\geq 18$  years of age at screening

### **Ethical**

- Before any study-specific procedures are performed, written informed consent must be obtained

### **5.3.2 Exclusion Criteria**

#### **Disease Related**

- Disease-associated symptoms requiring immediate therapy or other interventions
- Known brain metastases or cranial epidural disease unless adequately treated with radiotherapy and/or surgery and stable for at least 3 months before planned first dose of study drug

#### **Laboratory**

- Absolute neutrophil count <  $1.5 \times 10^9/L$
- Platelet count <  $100 \times 10^9/L$
- Hemoglobin < 9 g/dL
- Bilirubin > 1.5 X upper limit of normal (ULN)
- Aspartate aminotransferase (AST) or alanine aminotransferase (ALT) > 2.5 X ULN (OR > 5 X ULN in the presence of known liver metastases)
- Serum creatinine > 1.5 X ULN OR estimated creatinine clearance  $\leq 60$  ml/min (Cockcroft-Gault)
- Partial thromboplastin time (PTT) > 1.25 X ULN
- Prothrombin time (PT) > 1.25 X ULN OR international normalization ratio (INR) > 1.4

#### **Medications**

- Radiation therapy for bone metastasis within 2 weeks, any other external radiation therapy within 4 weeks before planned first dose of study drug. Systemic treatment with radionuclides within 6 weeks before planned first dose of study drug. Subjects with clinically relevant ongoing complications from prior radiation therapy are not eligible
- Prior treatment with everolimus, or any other specific or selective TORC1/PI3K/AKT inhibitor (e.g., temsirolimus)
- Receipt of any type of small molecule kinase inhibitor (including investigational kinase inhibitor) within 2 weeks before planned first dose of study drug
- Receipt of any type of anticancer antibody (including investigational antibody) within 4 weeks before planned first dose of study drug
- Taking strong inducers or inhibitors of CYP450s for subjects receiving everolimus
- Chronic treatment with corticosteroids or other immunosuppressive agents
- Concomitant anticoagulation at therapeutic doses with oral anticoagulants or platelet

inhibitors

- Subjects with a known hypersensitivity to everolimus or other rapamycins (sirolimus, temsirolimus) or to its excipients
- Not recovered from toxicities related to any prior treatments, unless adverse events are clinically non-significant and/or stable on supportive therapy

### **General**

- History of any medical, psychiatric, or social (e.g., addictive disorder) conditions, or laboratory abnormality that in the opinion of the investigator, may increase the risks associated with study participation or treatments that may interfere with the conduct of the study or the interpretation of study results
- Major surgery within 2 months before planned first dose of study drug. Complete wound healing from major surgery must have occurred within 1 month before planned first dose of study drug and from minor surgery at least 10 days before planned first dose of study drug
- Myocardial infarction within the previous 6 months before planned first dose of study drug
- Active infection requiring parenteral antibiotics within 2 weeks before planned first dose of study drug
- Diagnosis of another malignancy within 2 years before planned first dose of study drug, except for superficial skin cancers, or localized, low grade tumors;
- Currently enrolled in and has not yet completed at least 30 days since ending other investigational device or drug study before planned first dose of study drug, or subject is currently receiving other investigational agent(s).
- Prior or current history of hepatitis B, hepatitis C or human immunodeficiency virus
- Pregnant, planning a pregnancy or breastfeeding during the study
- Sexually active fertile subjects (male and female), must agree to use medically accepted methods of contraception during the course of the study and for 30 days after the last dose of study treatment. Female subjects must meet at least one of the following criteria:
  - be surgically sterile (i.e., have had bilateral tubal ligation, hysterectomy, or bilateral oophorectomy at least 6 months before enrollment; appropriate documentation will be required),
  - be post-menopausal for at least 12 months OR
  - if sexually active, be willing to use double-barrier contraception (e.g., condom with spermicide), intrauterine device, steroidal contraceptive (oral, transdermal, implanted, or injected) or other method, approved by the sponsor.
- Unwilling or unable to comply with study requirements or not available for follow-up assessments
- Any other major illnesses that in the investigator's judgment substantially increases the risk associated with the subject's participation in the study

